#### 4.3.8 Type and Duration of the Follow-Up of Subjects after Adverse Events

In so far as is possible, all individuals will be followed up until the AE or suspected ADR has been resolved. If an AE/suspected ADR/SAE is present when the subject has completed the study, the course of the event must be followed until the final outcome is known, or the event has been stabilized and no further change is expected and the Investigator decides that no further follow-up is necessary.

Any pregnancy must be followed by the Investigator until delivery or to the end of pregnancy.

### 4.4 Reporting of Serious Adverse Events or Pregnancy

#### 4.4.1 Reporting Serious Adverse Event

Any SAE (see [Section 4.3.6](#)) that occurs after **signing the study ICF through the Final Visit (ie, end of study)** must be expeditiously reported whether or not considered attributable to the study drug. Each SAE must be fully recorded in the subject's eCRF and SAE Report Form.

SAEs will be reported using the designated SAE Report Form. When the Investigator becomes aware of an SAE, she/he must submit a completed, signed and dated SAE Report Form (in English) **within 24 hours** to the Sponsor by email/fax.

Each SAE must be followed up until resolution or stabilization. After the initial report, all relevant information for SAE follow up, and for the outcome, must also be supplied to the Sponsor in a timely manner (within 3 days from its identification or within 24 hours for relevant new information) by means of the SAE Report Form. In addition, the Sponsor or contract research organization (CRO) may request additional information and/or reports.

All SAE Report Forms and Pregnancy Report Forms must be reported to:

Grifols Global Pharmacovigilance for Reporting SAEs and Pregnancy

Email: [REDACTED]

FAX (back-up only): [REDACTED] (US/Canada) and [REDACTED] (International)

When required, and according to local law and regulations, SAEs must be reported to the IRB/EC and regulatory authorities.

#### 4.4.2 Reporting Pregnancy

Pregnancies occurring during the course of the study will not be considered an AE unless a relation to the study drug is suspected. In any case, a Pregnancy Report Form must be completed and sent as soon as possible to the Sponsor for any pregnancies that occur from time of consent through the Final Visit (ie, end of study). A copy of the form should be filed at the study site for follow-up until the end of the pregnancy. Any pregnancy must be followed by the Investigator until delivery or to the end of pregnancy. Any anomalies, complications, abnormal outcomes, or birth defects observed in the child must be reported as an SAE (see email address or fax number in Section 4.4.1) within 24 hours of the Investigator or study personnel's first knowledge.

## 5 STATISTICAL METHODS AND DETERMINATION OF SAMPLE SIZE

### 5.1 Statistical and Analytical Plans

Unless otherwise specified, descriptive statistics will include the number of observations, mean, standard deviation (SD), median, minimum, and maximum values for the continuous/quantitative data or absolute and relative frequency counts and percentages for categorical/qualitative data.

Data handling and evaluation procedures will be described as detailed in the Statistical Analysis Plan.

#### 5.1.1 Subject Populations for Analysis

##### Safety Population

The safety population will include all subjects who received any amount of study drugs (IGIV-C 10% and/or IGSC 20%) and will be used for safety analysis.

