## 2.4 Safety Objective

- To assess the safety and tolerability of IGSC 20% as an IgG replacement therapy in subjects with PI

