### 3.1.2 Run-In Phase

#### Group 1 - Subjects are eligible for direct entry into the IV Phase:

Subjects who are already receiving a stable ( $\geq 3$  months) dose of IV IGIV-C 10% between 300 and 800 mg/kg per infusion every 3 or 4 weeks, do not need to enter the Run-In Phase and may proceed directly to the IV Phase. These subjects will have their IV#1 Visit scheduled to coincide with the date for their next IV infusion according to their regular dosing interval. The subjects will come to the clinic for this visit.

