#### Group 2 - Three (3)-month Run-In Phase:

Those subjects who prior to screening are receiving IVIG therapy (at a dose between 300 and 800 mg/kg per infusion every 3 or 4 weeks) but who are not receiving IGIV-C 10% specifically (ie, a different commercially available IVIG) will be required to receive IGIV-C 10% intravenously (at an equivalent dose and dosing interval as in their previous IVIG therapy) for a total duration of a 3-month Run-In Phase. Subjects receiving infusions every 3 weeks will have 4 Run-In visits and subjects receiving infusions every 4 weeks will have 3 Run-In visits.

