### 4.3.3 Causality of Adverse Event

The Investigator is required to provide a causality assessment for each AE reported to the Sponsor. The Sponsor will consider the Investigator's causality assessment. Assessment of the causal relationship to the study drug will be made according to the following classifications based on Karch FE et al. (39):

**Definite:** An event that follows a reasonable temporal sequence from administration of the treatment or in which the treatment level has been established in body fluids or tissues; and that is confirmed by improvement on stopping the treatment (dechallenge), and reappearance of the event on repeated exposure (rechallenge).

**Probable:** An event that follows a reasonable temporal sequence from administration of the treatment; that is confirmed by dechallenge; and that could not be reasonably explained by the known characteristics of the subject’s clinical state.

**Possible:** An event that follows a reasonable temporal sequence from administration of the treatment but that could have been produced by the subject’s clinical state or other modes of therapy administered to the subject.

**Doubtful/Unlikely:** An event that follows a reasonable temporal sequence from administration of the treatment; but that could not be reasonably explained by the known characteristics of the subject’s clinical state.

**Unrelated:** Any event that does not meet the criteria above.

The operational tool to decide the AE causal relationship is based on algorithms by Karch FE et al. and Naranjo CA et al. (40,41).

When an AE is classified, assessing causal relationship by the Investigator, as definitive, ie, “probable”, “possible” or “doubtful/unlikely”, the event will be defined as a suspected ADR. A suspected ADR with a causal relationship of “definite” will be defined as an AR. When the causal relationship is labeled “unrelated”, then it will be considered that the AE is not imputable to the study treatment and it is not a suspected ADR.

In addition, when a causal relationship between the study treatment and the AE cannot be ruled out by the Investigator and/or Sponsor, it means that the AE cannot be labeled “unrelated”.

For any subject, all AEs that occur at any time from the beginning of IP/study drug administration until the final visit of the clinical trial will be considered as treatment emergent AEs (TEAEs).

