### 5.1.6 Safety Analysis

The safety analyses are based on the safety population.

All AEs, suspected ADRs, ARs, SAEs, and discontinuations due to AEs and SAEs will be summarized by presenting the number of AEs and the number and percentage of subjects with AEs. The summaries will be presented by MedDRA system organ class and preferred term. AE summaries by severity will also be provided. Local infusion site reactions will be similarly summarized. Non-serious infections of any kind (including acute sinusitis, exacerbation of chronic sinusitis, acute otitis media, pneumonia, acute bronchitis, infectious diarrhea, etc.) as determined by the Investigator will also be considered a safety endpoint and will be similarly summarized.

Subjects with deaths, SAEs, and AEs leading to premature discontinuation from the study will be listed and presented in a narrative form.

Adverse events temporally associated with IV or SC administration of study drug will be defined as those occurring during or within 72 hours of completion of an infusion.

Additionally, local infusion site reactions will be tabulated and summarized for the total duration of the study and by IGSC 20% infusion week.

For all laboratory tests and vital signs, the original value and the change from Baseline will be summarized for numeric results and frequency/percentage will be summarized for qualitative results. For laboratory tests with normal ranges, out of normal range values will be flagged and shift tables will be provided.

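### Do the protocol's safety definitions force IGIV-C 10% and IGSC 20% adverse events into one pooled table?

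*Protocol*

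**What the plan says.** Section 2.4 sets the safety objective: "To assess the safety and tolerability of IGSC 20% as an IgG replacement therapy in subjects with PI". Section 5.1.1 defines the safety population: "The safety population will include all subjects who received any amount of study drugs (IGIV-C 10% and/or IGSC 20" [%)]. Section 5.1.6 adds: "The safety analyses are based on the safety population".

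The treatment-emergent window is defined in Section 4.3.3 as "all AEs that occur at any time from the beginning of IP/study drug administration until the final visit". Both products count as study drug, and every subject receives IGIV-C 10% first, in the Run-In Phase or at IV#1.

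Under Section 5.1.6, adverse events, suspected reactions, adverse reactions and serious events are "summarized by presenting the number of AEs and the number and percentage of subjects with AEs", by MedDRA class and preferred term, with a further summary by severity. No column structure and no split by phase is given. The same section defines events associated in time with an IV or SC infusion (72 hours) and summarises infusion site reactions by IGSC 20% infusion week.

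Section 4.3.7 requires date and time of onset for each adverse event. Section 5.1 leaves data handling and evaluation procedures to the statistical analysis plan.

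**The concern.** The objective names one product; the population and the treatment-emergent window cover two. If an analyst put every event since first dose over every treated subject, the resulting percentage would be neither an IGSC 20% rate nor an IGIV-C 10% rate.

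Two distortions would act together. Events from the Run-In and IV Phases would raise the count, by an amount that depends on how many subjects needed a run-in. Subjects who left before the first IGSC 20% infusion would stay in the denominator and dilute the subcutaneous events. One route to that is explicit: Section 3.7 withdraws a subject who has a serious bacterial infection before the first IGSC 20% dose, and that subject remains in the safety population.

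Section 5.2 says the sample size rests mainly on safety, and Section 5.1.5 promises annualised infection rates without naming the time at risk. A blurred safety summary would therefore affect a main purpose of the trial.

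**Working it through.** **1. The plan's own duration.** Section 3.6.1 gives participation of up to 50 weeks. The longest path is screening 4 + Run-In 16 + IV Phase 5 + SC Phase 24 = 49 weeks, taking the Run-In as 4 visits × 4 weeks. With four calendar months (17.4 weeks) the sum is 50.4. The stated figure lies between the two, so the phase lengths are consistent.

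**2. IGIV-C 10% time before SC#1.** Weeks = Run-In visits × interval + one IV interval + 1 week from IV#2 to SC#1. Visit counts come from Section 3.1.2: Group 1 subjects "do not need to enter the Run-In Phase and may proceed directly to the IV Phase"; for Group 2, "Subjects receiving infusions every 3 weeks will have 4 Run-In visits and subjects receiving infusions every 4 weeks will have 3 Run-In visits"; Group 3 has 5 visits (every 3 weeks) or 4 visits (every 4 weeks). Share = IV weeks / (IV weeks + 24).

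| Entry group | Interval | Run-In weeks | IGIV-C 10% weeks | Share of window |
|---|---|---|---|---|
| 1 | 3 weeks | 0 | 0 + 3 + 1 = 4 | 4/28 = 14% |
| 1 | 4 weeks | 0 | 0 + 4 + 1 = 5 | 5/29 = 17% |
| 2 | 3 weeks | 4 × 3 = 12 | 12 + 3 + 1 = 16 | 16/40 = 40% |
| 2 | 4 weeks | 3 × 4 = 12 | 12 + 4 + 1 = 17 | 17/41 = 41% |
| 3 | 3 weeks | 5 × 3 = 15 | 15 + 3 + 1 = 19 | 19/43 = 44% |
| 3 | 4 weeks | 4 × 4 = 16 | 16 + 4 + 1 = 21 | 21/45 = 47% |

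The 21-week figure is right, but it is the maximum and applies only to Group 3 on 4-week dosing. The mix of entry groups is not given.

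**3. What one pooled table would do (assumed rates).**
- Event rate: let r be the weekly rate on IGIV-C 10% relative to IGSC 20%. The pooled rate relative to the SC rate is (IV weeks × r + 24)/(IV weeks + 24). At 21 IV weeks, r = 0.5, 1 and 2 give 34.5/45 = 0.77, 1.00 and 66/45 = 1.47. At 4 IV weeks they give 26/28 = 0.93, 1.00 and 32/28 = 1.14.
- Incidence: with an assumed constant hazard of 0.01 per week, 1 − exp(−0.45) = 36% over 45 weeks against 1 − exp(−0.24) = 21% over 24 weeks.
- Denominator: if 50 subjects were treated and only 42 to 48 (the completer targets, used here as an assumption) received IGSC 20%, subcutaneous percentages would read at 42/50 = 84% to 48/50 = 96% of their true value.

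**4. Does the protocol call for that table?** Set side by side, the passages do not.
- Section 5.1.1 says who belongs to the population. A population covering both products can be tabulated in separate phase columns, each with its own number exposed.
- Section 5.1.6 says what is counted and never uses the term treatment-emergent. Read as a complete table specification, its reference to all adverse events would also take in events between consent and first dose, which Section 4.3.1 requires to be recorded. It is a list of content, not a layout.
- Section 4.3.3 separates events before first study drug from those after. It does not prevent a further cut at SC#1.
- Sections 3.1.3 and 3.1.4 make the phases sequential, and Section 4.3.7 dates each onset. Assignment to a product therefore needs no new data.

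**The case for a change.** The best case for a change is that these definitions sit in the protocol and do not depend on the analysis plan. No stated population is limited to IGSC 20% recipients. The protocol does separate the periods when it wants to: PK parameters are calculated separately by route (Section 5.1.3), site reactions are shown by IGSC 20% week (Section 5.1.6), and the stopping rule counts subjects on IGSC 20% (Section 3.9). The main adverse-event tables carry no such instruction, so a literal analyst could pool. A sentence would cost little.

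Part of this stands. The protocol is silent on a phase split for adverse events and on the time at risk for the annualised infection rates, and a statement of both would be tidier. But the same examples also show that the authors recognise the distinction by route, which makes a pooled headline table less likely. Silence about columns and per-phase denominators is ordinary in a protocol that hands evaluation procedures to its analysis plan. The further claim, that the IGSC 20% safety objective could not be answered, does not stand, because every event can be placed before or after the first IGSC 20% infusion.

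**Conclusion.** The concern describes a real mismatch of scope: a population and window covering two products, and an objective covering one. It does not identify anything the protocol states wrongly. Pooling is an inference from silence, and what is missing is table layout, which analysts would ordinarily settle in the analysis plan by showing the SC Phase separately over subjects who received IGSC 20%.

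The sizes depend on that inference. The 14% to 47% share of IGIV-C 10% time is sound arithmetic from the visit schedule, but it becomes a distortion only in a single pooled table. The hazard, the rate ratios and the number never reaching IGSC 20% are assumptions with no source in the protocol. The conclusion rests on the analysis plan, not available here, making the ordinary split by phase. Nothing in the protocol prevents it from doing so, and no change to the plan is needed.

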##### PK Population

The PK population will consist of all subjects who receive study drugs and have sufficient and valid total IgG concentration vs. time data for either the IV or SC Phase to allow calculation of  $AUC_{0-\tau,SC}$  or  $AUC_{0-\tau,IV}$  (the primary PK endpoint).

The validity of total IgG concentrations will be reviewed and determined before the database lock based on consideration of treatment compliance and blood sampling/testing issues (such as collection problem). Any invalid total IgG concentrations will be flagged with the reason for invalidity in the listing.

## IgG Population

The IgG population will consist of all subjects who receive study drugs and have any total IgG concentration data. The summary of total IgG concentration data will be based on IgG Population.

### 5.1.2 Demographic and Baseline Characteristics

The demographic and baseline characteristics will be summarized. For quantitative variables, mean, SD, median, and minimum/maximum will be provided. For qualitative variables, the frequency and percentage will be provided.

### 5.1.3 Pharmacokinetic Analysis

All subjects in the PK Population as defined above will be included in the PK analysis. Total IgG concentrations will be summarized for IV and SC by each timepoint. Individual and mean total IgG concentrations vs. time curves will be plotted. PK parameters of total IgG will be determined by noncompartmental PK methods using WinNonlin Professional version 6.4 or above (Pharsight Corporation, Cary, NC). Steady-state PK parameters to be calculated, as appropriate, or as permitted by data, will include AUC,  $C_{max}$ , and  $t_{max}$ . All PK parameters will be calculated separately for IV and SC administration and will be tabulated and summarized descriptively. The mean and the lower and upper bounds of the 90% CI will be calculated on ln-transformed AUC parameters. These mean and lower and upper bounds will be back-transformed (exponentiated) to provide the geometric mean and 90% CI on the original scale.

The Primary PK endpoint is the steady-state AUC over a dosing interval defined as follows:

- $AUC_{0-\tau,SC}$ , the AUC over a weekly dosing interval ( $\tau$ ) at an approximate steady-state condition following weekly SC infusion, ie,  $AUC_{0-7 \text{ days}}$ .
- $AUC_{0-\tau,IV}$ , the AUC over a regular dosing interval ( $\tau$ ) at an approximate steady-state condition following the regular IV infusion, either every 3 weeks or every 4 weeks, ie,  $AUC_{0-21 \text{ days}}$  or  $AUC_{0-28 \text{ days}}$ , respectively.

$AUC_{0-\tau,SC}$  is to be obtained after the 13th SC dose of IGSC 20% at the weekly dose calculated using the final dose adjustment factor, and  $AUC_{0-\tau,IV}$  is to be obtained following IV infusion of IGIV-C 10% at the IV#1 visit. Since the dosing interval ( $\tau$ ) is 7 days for the SC dose,  $AUC_{0-\tau,SC}$  is determined as  $AUC_{0-7 \text{ days}}$ . For IV dosing, the dosing interval ( $\tau$ ) is 21 or 28 days for the 3-week or 4-week subjects,  $AUC_{0-\tau,IV}$  is determined as  $AUC_{0-21 \text{ days}}$  or  $AUC_{0-28 \text{ days}}$ , respectively.

Prior to statistical comparison of  $AUC_{0-\tau}$ 's between the IV IGIV-C 10% and SC IGSC 20% doses, the  $AUC_{0-21 \text{ days}}$  from the IV infusion in subjects on a 3-week IV dosing interval will be divided by 3 or the  $AUC_{0-28 \text{ days}}$  from IV dosing in subjects on a 4-week IV dosing interval divided by 4 for comparison with  $AUC_{0-7 \text{ days}}$  from the weekly SC infusion.

The hypothesis to be tested is that the weekly SC dose of IGSC 20% will achieve an approximate steady-state  $AUC_{0-\tau,SC}$  of total IgG that is non-inferior to that achieved by a regular IV dose of IGIV-C 10% ( $AUC_{0-\tau,IV}$  divided by 3 or 4 depending on the IV dosing intervals). Non-inferiority of steady-state IgG AUC between SC dose of IGSC 20% and IV IGIV-C 10% administration will be tested based on established regulatory guidelines for bioequivalence testing. The 90% CI of the geometric LSM ratio of SC AUC to IV AUC will be calculated. The SC dose is considered to be non-inferior to the IV dose if the low bound of the 90% CI for the geometric LSM AUC ratio is above 0.80 based on loge-transformed data.

### Secondary and Exploratory PK Analysis

Secondary and exploratory PK endpoints include the steady-state mean trough concentration of total IgG and the  $C_{max}$ ,  $t_{max}$  of total IgG. Descriptive statistics will be calculated for the steady-state mean trough concentration of total IgG and for the  $C_{max}$ , and  $t_{max}$  of total IgG. All pre-infusion total IgG concentrations obtained before and at the 13th SC dose of IGSC 20% will be evaluated to determine if an approximate steady-state condition has been achieved by the 13th SC dose. The steady-state mean trough concentrations of total IgG following SC administrated IGSC 20% will be determined as the average value of  $C_{trough}$  measurements obtained at Weeks#13, #14, #17, and #21. The average steady-state trough concentrations of total IgG following IV administrated IGIV-C 10% will be determined as the average value of  $C_{trough}$  measurements obtained at the IV#1 visit and at 21 or 28 days after the IV#1 IGIV-C 10% dose (depending on dosing interval), ie, immediately prior to the administration of IV dose at IV#2 visit.

Summaries will be provided for trough concentration of total IgG and each of its subclasses between IV infusion of IGIV-C 10% and SC administration of IGSC 20%. Summaries of trough level concentration of antibody titers against *S. pneumonia*, *H.influenza*, and *C. tetani* will also be provided.

Depending on the number of subjects being dosed on IGIV-C 10% at 3- or 4-week dosing intervals, subgroup analyses may be performed to evaluate PK variables by IV dosing interval. Subgroup analyses will additionally include age, sex, race, ethnicity and other factors as appropriate.

#### 5.1.4 Interim PK Analysis

An interim PK analysis will be conducted as described in [Section 3.1.5](#). This analysis will be performed as soon as practical after the first 6 adult/adolescent subjects (aged  $\geq 12-75$  years) have completed the PK sampling schedule for both the IV and SC (after the 13th SC dose) Phases of the trial. PK data from these 6 adult/adolescent subjects will be analyzed using procedures as described in [Section 5.1.3](#) above. A decision on whether to modify the dose adjustment factor for calculating the SC dose will be made based on this interim PK analysis.

Final PK and statistical analysis will be based on the PK data obtained after the final (or adjusted, if any) SC dose administered in all completed subjects.

### 5.1.5 Exploratory Analysis

Other exploratory variables include the following:

- Serious bacterial infections
- All infections of any kind (serious/nonserious including acute sinusitis, exacerbation of chronic sinusitis, acute otitis media, pneumonia, acute bronchitis, infectious diarrhea, etc.) which will be recorded as an AE with the Investigator answering the following question affirmatively in the eCRF: “Is this an infection? (verbatim term delineating infection).
- Validated infections documented by positive radiograph, fever ( $>38^{\circ}\text{C}$  oral or  $>39^{\circ}\text{C}$  rectal), culture, or diagnostic testing for microorganisms, eg, bacterial, viral, fungal or protozoal pathogens (for instance, rapid streptococcal antigen detection test).
- Number of days on antibiotics (including oral, parenteral, oral plus parenteral, prophylactic and therapeutic). Use of prophylactic antibiotics will be distinguished from antibiotics for treatment of acute infection.
- Number of hospitalizations due to infection
- Number of days of work/school/daily activities missed due to infections and their treatment.

These parameters will be summarized descriptively. The number and proportion of subjects having any SBI, infections, days on antibiotics, hospitalizations due to infection, and days of work/school/daily activities missed due to infections will be calculated and summarized. Furthermore, the total number of events or days and corresponding annualized rate per subject of SBIs, infections, days on antibiotics, hospitalizations due to infection, and days of work/school/daily activities missed due to infections will be calculated and summarized.

